#### PK Sampling

Blood samples will be used to establish population pharmacokinetics. Scavenged blood samples of 0.05 mL of blood will be collected from all clinical blood draws throughout the infant’s hospitalization and sent to the University of Iowa for population pharmacokinetics using meso-scale discovery assay to detect Epo levels. Since a baseline sample is also required for immunogenicity testing we will collect an extra 0.3 mL of blood with the “pre-drug” blood work drawn in the NICU. Study participants will have the option of opting in for this additional blood draw. This will ensure that there is enough blood for potential immunogenicity testing and pK analysis. Every effort will be made to obtain this sample with a blood draw that is needed for clinical purposes (such as a glucose check). All other pk samples will be off of scavenged blood. Parents will be given the option to opt into this part of the study on the consent form.

Parents of participants will be contacted by phone call at 4 months of age which will include developmental screening via a modified Ages and Stages questionnaire (attached), number of hospitalizations, seizures, need for assisted respiratory support, failure to thrive, medication use, use of early intervention services, hearing impairment, any concern with vision.

Participants will have neurodevelopmental testing (Bayley III and Gross Motor Function Assessment) performed at 8-12 months of age. We will also conduct a brief medical exam including weight, length, head circumference, blood pressure, and heart rate.

In addition, we may contact the child’s primary care provider and ask for the baby’s most recent medical history and the result of the most recent hematocrit.

Data will be kept for analysis for up to 10 years.

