**MEND (Mild Encephalopathy in the Newborn treated with Darbepoetin)**

11.18.2020

Evaluation	Screening	Pre-Entry (Prior to 24 hrs)	Entry (<24 hr of age)	discharge, transfer, or 96 hours of age (which ever occurs first)	3-10 days	Discharge	4 months corrected age	8-12 months corrected age
Screen admissions to NICU	X	X						
Documentation of Gestational Age		X						
Informed Consent		X						
Maternal Demographics and History			X			X		
Blood Pressure			X		X	X		X
Modified Sarnat Exam				X				
MRI as available from clinical care					X	X		
Hematology (CBC/transfusions/phlebotomy loss) as available from clinical care			X			X		X
Administration of study drug IV			X					
Liver/kidney Function Tests (as clinically available)					X			
Complete Physical Exam including weight, head circumference and length			X			X		
Telephone contact to review current status							X	
Ages and Stages phone questionnaire							X	
Phone/in person survey on hospitalizations, seizures, need for respiratory support, failure to thrive, medication use, use of early intervention, hearing impairment, concerns with vision							X	X
Neurodevelopmental assessment Bayley III & Standardized Neurologic exam								X
Weight, length, head circumference, blood Blood pressure, and heart rate								X

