### **5. Data Analysis**

This will be a multicenter pilot/feasibility trial to assess Darbe for infants who do not qualify for TH. Data from this trial will be used to power a large multicenter RCT. Primary outcome variable will be the incidence of abnormal neurodevelopmental score by Bayley III <85 or GMFS of >1 at 8-12 months of age. Chi-square or Fisher exact statistical tests will be performed for all categorical values. For continuous variables, t tests will be performed. All outcomes will be analyzed based on intention to treat inclusion of all randomized patients. We estimate infants who received Darbe will experience an estimated 30% decrease in neurodevelopmental impairment, defined as BSID III cognitive score or motor score <85, or a Gross Motor Function Classification Scale score >1. A total of 40 infants per group will be required to identify a 30% difference between groups.

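### Section 5 plans only t tests for continuous measures; adjusting for the pre-dose value where one exists would sharpen these secondary and safety comparisons at almost no cost (minor)

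*Combined protocol and SAP*

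**What the plan says.** Section 5 (Data Analysis) assigns chi-square or Fisher tests to categorical variables and then says: "For continuous variables, t tests will be performed". It names no covariate, change score or repeated-measures model, and none appears elsewhere.

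The schedule of evaluations in Section 3 marks these measures more than once:

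- The row "Blood Pressure" is marked at entry, 3-10 days, discharge and 8-12 months.
- The row "Hematology (CBC/transfusions/phlebotomy loss) as available from clinical care" is marked at entry, discharge and 8-12 months.
- The row "Complete Physical Exam including weight, head circumference and length" is marked at entry and discharge. Growth is measured again at 8-12 months, where the follow-up text under PK Sampling plans a "brief medical exam including weight, length, head circumference, blood pressure, and heart rate".

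The 8-12 month growth and blood pressure measurements are listed as research procedures. In-hospital vital signs, hematocrit and physical examination are different: the Data collection paragraph records them only when they are done for clinical reasons. The late hematocrit is the most recent value held by the primary care provider, with no fixed time.

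Section 8 lists rises in red cells and blood pressure among the risks seen in adults. Growth is not listed. The primary outcome is binary: "Primary outcome variable will be the incidence of abnormal neurodevelopmental score by Bayley III <85 or GMFS of >1 at 8-12 months of age".

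**The concern.** When a measure is taken before treatment and again afterwards, the infant's own earlier value usually explains part of the later spread. A t test on the later value leaves that part in the error term. With at most 40 infants per arm, the interval around a difference in mean blood pressure or hematocrit will already be wide.

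Two features of the protocol make the point relevant. The Safety paragraph defines an adverse event as a change from the infant's baseline condition, so the baseline is already part of the safety concept. Section 5 also says the data will be used to power a larger trial, for which a baseline-adjusted residual SD is a useful design input. What is at stake is precision on secondary and safety measures, not the validity of any comparison.

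**Working it through.** **The plan's own figure.** Section 5 states "A total of 40 infants per group will be required to identify a 30% difference between groups" and "We estimate infants who received Darbe will experience an estimated 30% decrease in neurodevelopmental impairment". It gives no control rate, alpha or power, and does not say whether the 30% is absolute or relative. The usual formula is n = [z(α/2)√(2p̄(1−p̄)) + z(β)√(p₁(1−p₁) + p₂(1−p₂))]² / (p₁−p₂)². I assume two-sided 0.05, 80% power and an absolute drop from 50% to 20%:

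[1.96 × √0.455 + 0.8416 × √0.41]² / 0.09 = 3.463 / 0.09 = 38.5, so 39 per group.

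Drops from 55% to 25% and from 60% to 30% give 41 and 42. A relative 30% drop gives 285 per group at a 36% control rate and 170 at 50%. So 40 is attainable, but it cannot be reproduced from the document's own inputs. Nothing below depends on how it was derived.

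**Precision with and without the entry value.** Inputs: 40 per arm (Section 5); the entry-to-later correlation r is assumed over a range because the documents give none; two-sided 0.05 and 80% power are assumed; data are taken as complete.

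- Adjusted variance relative to the t test: 1 − r². The share removed is r².
- Interval width relative to the t test: √(1 − r²).
- Equivalent t-test size: 40 / (1 − r²) per arm.
- Detectable difference in SD units: (1.96 + 0.8416) × √(2/40) × √(1 − r²) = 0.626 × √(1 − r²).

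| Assumed r | Relative variance | Variance cut | Relative width | Equivalent per arm | Detectable difference (SD) | Power for 0.5 SD |
|---|---|---|---|---|---|---|
| 0 (t test) | 1.00 | 0% | 1.000 | 40.0 | 0.626 | 61% |
| 0.1 | 0.99 | 1% | 0.995 | 40.4 | 0.623 | 61% |
| 0.2 | 0.96 | 4% | 0.980 | 41.7 | 0.614 | 63% |
| 0.3 | 0.91 | 9% | 0.954 | 44.0 | 0.598 | 65% |
| 0.5 | 0.75 | 25% | 0.866 | 53.3 | 0.543 | 73% |
| 0.7 | 0.51 | 49% | 0.714 | 78.4 | 0.447 | 88% |

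**Cost of estimating the slope.** With n per arm the expected inflation is about 1 + 1/(2n − 4), which is 1 + 1/76 = 1.013 at n = 40. At r = 0.1 the net relative variance is 0.99 × 1.013 = 1.003, and at r = 0.2 it is 0.96 × 1.013 = 0.973. Low correlations therefore bring about nothing, but also cost almost nothing.

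**A t test on change from entry.** With equal SDs at the two times its relative variance is 2(1 − r): 1.4 at r = 0.3, 1.0 at r = 0.5 and 0.6 at r = 0.7. Below r = 0.5 it is worse than ignoring the entry value. Apart from the slope cost, the adjusted model is never worse than either.

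**Missing values.** If only 30 infants per arm had a later value (an assumption), the t test would detect 2.8016 × √(2/30) = 0.723 SD, and the adjusted model at r = 0.5 would detect 0.723 × 0.866 = 0.626 SD. Losing a quarter of the later values therefore cancels the whole gain from r = 0.5. At 20 per arm the figures are 0.886 and 0.767 SD.

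**The case against.** The strongest reply is that the plan may never compare these means. Section 5 names none of the five measures as an outcome. The Safety paragraph looks for adverse events and values outside the normal range, and Section 6 treats hematocrit and hypertension as thresholds. Such findings are counts and fall under the chi-square or Fisher rule. This stands, and it limits the point to whatever between-arm comparisons of continuous measures are made. For those, the t-test sentence is the only rule.

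Four stronger readings are tempting, and the documents do not support them.

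- A reader might infer that the entry values are thrown away. Section 5 is silent on them, and a t test on change would still be a t test. What can be said is that no use of them is planned.
- A reader might infer that a chance imbalance at entry makes the t test wrong. Under randomisation it is unbiased, and its error rate already allows for chance imbalance. Only efficiency is lost.
- A reader might link all five measures to the drug's named risks. Only blood pressure and hematocrit have that link.
- A reader might take the schedule to mean that every infant has a usable pair. In-hospital values and hematocrit depend on clinical care. The entry column also contains drug administration and does not say that the measurements come first. The hematocrit limit among the exclusions, the weight-based dose and the statement that most admitted infants have a blood count on admission make pre-dose values likely, but not certain.

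Finally, one correlation cannot serve all measures and intervals. First-day blood pressure or hematocrit may say little about values at 8-12 months.

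**Conclusion.** The point holds as a minor, nearly free improvement, not as an error in the plan. The adjusted analysis removes r² of the variance: from 1-4% at r = 0.1-0.2, roughly nil after the slope cost, through 9% at 0.3 and 25% at 0.5 to 49% at 0.7. These figures apply among infants with a later value and are reached in full only if their pre-dose values are also present. The correlation is an assumption throughout. The gain is probably larger at 3-10 days and discharge, days after entry, than at 8-12 months. Missing later values may matter more than the choice of test. The binary primary outcome has no entry counterpart, so it and the sample size of 40 per group are unaffected.

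**What to change.** In Section 5:

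- State which continuous measures will be compared between arms and at which time point.
- Compare each measure that has a pre-dose value by a linear model of the later value on arm and the last value recorded before the dose.
- Fill any missing pre-dose covariate (blood pressure and growth as well as hematocrit) with the all-infant mean, blind to arm. This is acceptable because the value precedes treatment; it costs some precision but does not favour an arm.
- Keep the t test for measures with no pre-dose value, such as Bayley scores.
- Report the number of infants in each arm with a later value at each time point. Filling the covariate does nothing for a missing outcome.

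The cost is a few lines of text and trivial programming. No visit, blood sample or infant is added. The data collection form should record whether each entry value was taken before the dose.

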## **MEND (Mild Encephalopathy in the Newborn treated with Darbepoetin)**

11.18.2020

(10 µg/kg IV), or placebo. **We plan to enroll 20 participants at the University of New Mexico.** A total of 80 infants at all sites (see table below) will be enrolled.

[name] (PI) Holds the IND for Darbepoetin and mild NE (IND 132207) and will remain as a study team member and overall PI of this multi-center study. Treatment will be randomized by the pharmacy and blinded to the caregivers. All groups will receive the dose within 24 hours of birth.

✓		Intervention
Experimental groups Darbe	N=40	10 mcg/kg/dose Darbe IV <24 hours of age
Control group Placebo	N=40	Normal saline placebo dose IV at <24 hours of age

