### **Safety**

For the purpose of this study, an **adverse event** (AE) will be defined as any adverse change from the patient's baseline condition that occurred following the administration of the study drug through the end of the study period. Safety will be evaluated during the first 7 days of life or until hospital discharge (whichever comes first) by documenting potential adverse events such as (but not limited to) alterations in blood pressure, secondary infections, neutropenia, thrombotic/vascular events, hematologic events (platelets, Hct level, polycythemia), and hepatic/renal function that are outside of normal range for the study population.

We will assess for the rare complication (1 in 10,000 in adults with renal failure) of pure red blood cell aplasia. The vast majority of babies admitted to the NICU have a CBC with diff drawn on admission. If there is at least 0.5mL of blood remaining (scavenged blood) after analysis, we will collect that blood and use as our baseline sample. Similarly, most babies admitted to the NICU have electrolytes or bilirubin levels drawn at 24-72 hours of age, if there is at least 0.5mL of blood remaining (scavenged blood) after analysis, we will collect that blood and use as our second sample. If the baby remains in the NICU for 2 weeks (uncommon) and has a blood test done for clinical reasons, we will attempt to keep 0.5mL (scavenged blood) to assess for pure blood cell aplasia. Additionally, a letter (attached) will be given to the PCP stating that the patient is enrolled in a research study. If there are concerns for anemia and the PCP orders a CBC within the first year of life we will ask for 0.5mL of blood (scavenged blood). We will ask the lab to hold "scavenged" blood and store for up to 6 months beyond enrollment of the last patient.

We will also ask for the medical records from the child's primary care provider and their most recent hematocrit/hemoglobin.

**Long Term Safety** will involve phone calls at 4 months of age which will include developmental screening via Ages and Stages questionnaire, hospitalizations, seizures, need for assisted respiratory support, failure to thrive, medication use, use of early intervention services, hearing impairment, any concern with vision. In addition we will contact the child's primary care provider and ask for the child's medical records and most recent hematocrit/hemoglobin to assess for safety.

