**Serious adverse events** (SAE) will be defined as any event that results in: death, a life threatening event (major venous thrombosis, stroke, and/or severe hypertension), persistent or significant disability/ incapacity, and/or prolongs inpatient hospitalization.

SAEs will be reported until 30 days following final cessation of therapy or until hospital discharge, whichever comes first.

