### **6. Provisions to Monitor the Data to Ensure the Safety of Subjects**

The data and safety monitoring board (DSMB) is composed of members qualified by training and experience to monitor the progress of the investigation:

- 1) [name] Professor of Neurology, University of New Mexico. [name] will be the DSMB Chair for this project.
- 2) [name]. Professor of Pediatrics, University of New Mexico. [name] has led and conducted multiple multicenter clinical studies .
- 3) [name]. Division of Neuroscience, Department of Pediatrics, University of New Mexico
- 4) [name]. Professor of Pediatrics, Nationwide Children's Hospital, Columbus, Ohio.

Monitoring plan will include:

- 1) The DSMB will review the study data for non-compliance and participant safety (adverse events, unanticipated problems, etc.) after the first 20 patients have been enrolled and every 6 months until study completion

- 2) The DSMB will report their findings to the sponsor-investigator after each meeting
- 3) The sponsor-investigator will report DSMB findings to all participating clinical investigators after each meeting. Each participating investigator will submit the DSMB review to their IRB with corresponding documentation of the submission sent to [name]
- 4) All SAEs will be reported to [name] within 24 hours of the site learning of the event. Each site PI will be responsible for reporting the serious or unexpected adverse events to their local IRB in accordance with the local IRB policies. [name] will be responsible for notifying the DSMB chair within 24 hours of receiving the report and notifying the FDA in an IND safety report in accordance with FDA regulations. The DSMB will determine if the adverse event changes the risk to study subjects. If the information changes the known risk to subjects, the DSMB report of this event will be released to all participating investigators by [name].
- 5) Criteria for Withholding Study Drug: Neutropenia (ANC <500/ $\mu$ L), hematocrit of >65%, stroke, symptomatic clot, or hypertension (blood pressure 2 SD greater than the mean for age).

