#### ***Subjects who are not yet adults (infants, children, teenagers)***

This study involves children from age 0 to 12 months.

Written consent will be obtained by an investigator in a room which ensures the privacy of the family, and which is free of potential coercive influences. Consent for participation must be obtained by the time the baby is 24 hours of age.

If a family has limited or no English speaking abilities, a certified interpreter will be provided. They will review the consent form with the family, and interpret the verbal explanation of the study during the discussion between the investigator and the family members. If individual sites have a large population of non-English speakers, consent forms will be translated into the appropriate languages. If an interpreter is not available in a timely manner, the family will not be approached.

The parents of the research participants will be given opportunity to review the study both verbally and in writing. They will be given opportunity to ask questions of the investigator prior to giving consent.

If there are changes in the protocol or safety information that require consent forms to be updated, they will be sent through the IRB process for approval. The study entry form has a space for documentation of a signed consent form as well as a signed HIPAA form.

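### No safety population is defined: read literally, the all-randomised rule keeps undosed infants in the adverse-event denominator although they cannot have an event

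*Combined protocol and SAP*

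**What the plan says.** **Analysis set.** Section 5 (Data Analysis) states: "All outcomes will be analyzed based on intention to treat inclusion of all randomized patients". The site section repeats intention to treat for the data sent for analysis. No safety, as-treated or dosed population is defined anywhere.

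**Adverse events.** Section 3 (Safety) limits an adverse event to a change from baseline that "occurred following the administration of the study drug through the end of the study period".

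**Serious adverse events.** The same section says that these "will be defined as any event that results in: death, a life threatening event", followed by further outcomes, with no dosing condition in the definition. The reporting window, however, is tied to treatment: "SAEs will be reported until 30 days following final cessation of therapy or until hospital discharge, whichever comes first".

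**Dosing.** The trial gives one dose. Section 3 (Design) says: "All groups will receive the dose within 24 hours of birth". Section 7 (Withdrawal of Subjects) expects every eligible, consented infant to be dosed, and also lets families leave whenever they choose. Section 6 nevertheless contains a list headed "Criteria for Withholding Study Drug", which names neutropenia, high hematocrit, stroke, symptomatic clot and hypertension. Section 15 says: "Consent for participation must be obtained by the time the baby is 24 hours of age".

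**The concern.** Intention to treat is the right rule for the Bayley and gross motor outcomes, which can be observed in every randomised infant. It fits badly with an event that is defined as happening after dosing. An infant who is randomised and then not dosed adds one to the denominator and, by definition, nothing to the numerator. On any absolute adverse-event rate the error can only go one way, towards fewer apparent harms.

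The protocol leaves room for such infants. Because there is only one dose, the withholding list can only act before it, and a withheld dose may mean that the infant is never dosed. Neutropenia and high hematocrit are also exclusion criteria in Section 3. Stroke, symptomatic clot and hypertension are not, so an eligible infant can meet one of them. Withdrawal between randomisation and dosing is a second route.

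At stake are the adverse-event rates and upper limits that this Phase II trial would pass on to the larger trial that its data are meant to support.

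**Working it through.** **1. Inputs.** The arm size of 40 is from Sections 3 and 5. Section 5 gives no control rate, significance level or power, so 40 cannot be rebuilt from its own inputs. It is used here only as the denominator. The plan states no adverse-event rate, denominator or confidence limit that could be reproduced. Two inputs are therefore assumptions: the true rate among dosed infants (20%, for illustration) and the number *k* undosed in an arm (0 to 4, with 8 as a stress value).

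**2. Formulas.**
- Rate reported on all randomised = rate in dosed × (40 − k)/40. Each undosed infant costs 1/40 = 2.5% in relative terms.
- One-sided 95% upper limit with no events = 1 − 0.05^(1/n). This is 7.2% at n = 40 whatever *k* is, if all randomised infants are counted.

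**3. One arm.**

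| k undosed | n dosed | 20% rate reported as | zero-event limit on dosed | zero-event limit on 40 |
|---|---|---|---|---|
| 0 | 40 | 20.0% | 7.2% | 7.2% |
| 1 | 39 | 19.5% | 7.4% | 7.2% |
| 2 | 38 | 19.0% | 7.6% | 7.2% |
| 4 | 36 | 18.0% | 8.0% | 7.2% |
| 8 | 32 | 16.0% | 8.9% | 7.2% |

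**4. Between arms.** Assume 20% on Darbe and 5% on placebo among dosed infants: a difference of 15 points and a risk ratio of 4.0.
- Four undosed in each arm: 18.0% against 4.5%. The difference is 13.5 points and the ratio is still 4.0.
- Four undosed on Darbe only: 18.0% against 5.0%. The difference is 13.0 points and the ratio 3.6.
- Four undosed on placebo only: 20.0% against 4.5%. The difference is 15.5 points, so here the comparison moves the other way.

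Caregivers are blinded, and a decision not to dose comes before the product is given. Unequal numbers should therefore arise only by chance, and the first case is the one to expect.

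**The case against.** **Section 5 never mentions safety.** The rule follows a neurodevelopmental primary outcome. Section 3 evaluates safety by recording events, and Section 6 sends them to the data and safety monitoring board. No comparative adverse-event analysis is described, and safety is not among the three specific aims. This stands in part: a reader might infer that the plan expressly orders a safety analysis by intention to treat, and it does not. But the rule covers every outcome and no other rule exists, so the literal reading is the only one on offer.

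**There may be no undosed infants.** Section 7 says that eligible, consented infants get the drug. This stands as to size: zero belongs in the range. It does not settle the matter, because the withholding list in Section 6 points the other way. The timing of that check relative to randomisation is not stated. If it comes first, such an infant never enters the denominator.

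**Late consent.** A reader might infer that consent close to 24 hours produces randomised infants who can no longer be dosed. The documents do not show this: they nowhere say that an infant is randomised once dosing has become impossible. The consent deadline and the dosing window still need reconciling.

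**Both arms are treated alike.** A reader might infer that the rule hides harm from Darbe relative to placebo. It does not in general: placebo is diluted too, and with equal numbers undosed the risk ratio does not move.

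**Serious adverse events.** Their definition has no dosing condition, so an undosed infant can have one. How the reporting window applies to an infant without therapy is unclear, but the argument cannot simply be carried over.

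**Pharmacokinetics and power.** A reader might extend the point to the pharmacokinetic aim. Population pharmacokinetics models measured concentrations and is not an arm comparison, so that reading is strained. Low power to compare harms at 40 per arm is a separate matter, which a change of analysis set would not cure.

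**Conclusion.** The point holds as a flaw in the stated rule, with a small and uncertain effect. The two sentences read together, with no safety set defined, put infants who cannot have an adverse event into its denominator. Absolute rates in either arm, and their upper limits, are then too low. The risk difference shrinks when equal numbers are undosed, while the risk ratio is unchanged.

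The size rests wholly on the number undosed, which the documents do not give. At zero there is no effect. With 1 to 4 of 40 undosed, a 20% rate is reported as 19.5% to 18%, and a zero-event upper limit of 7.4% to 8.0% is reported as 7.2%. The conclusion applies to adverse events as Section 3 defines them, and less clearly to serious adverse events. It justifies a cheap improvement to the text and does not suggest that the safety results would be seriously misleading.

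**What to change.** In Section 5:

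- Keep intention to treat in all randomised infants for the neurodevelopmental outcomes.
- Analyse adverse events and laboratory safety in all infants who received study drug, by product received, and report rates and risk differences with exact 95% intervals.
- Report the number randomised but not dosed, per arm, with reasons, and list any serious adverse events in these infants separately.

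Two pairs of statements must also be reconciled: the expectation in Section 7 that the drug will be given with the withholding list in Section 6; and the consent deadline in Section 15 with the dosing window in Section 3 (Design and Research-Related procedures). How they are resolved is for the sponsor and the investigators.

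The cost is a few sentences and no new data, though Section 4 requires approval by each site's IRB of record before a modification is implemented. Safety denominators become slightly smaller, and the safety comparison is no longer strictly the randomised one. Because non-dosing is decided under blinding and before the product is given, that loss should be small.
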